Hypothesis: Patients who receive the ADL-enhanced program plus usual rehabilitation therapy will show greater improvements in the Motor Skills scores of the Assessment of Motor and Process Skills (the primary outcome), Self-care items in the Outcome and Assessment Information Set (clinical outcome), and Activity Measure for Post-Acute Care Home Health Short Form (patient-reported outcome) at treatment completion and less decline at 1-month and 3-month follow-up than usual rehabilitation therapy.

Secondary Objectives.

Secondary objective 1: To estimate the preliminary effect of the ADL-enhanced program on improving physical functioning at treatment completion and one month after the completion.

Hypothesis 1: Patients who receive the ADL-enhanced program plus usual rehabilitation therapy will show greater improvements in the Box and Block Test (upper extremity physical function), Jebsen Hand Function Test (upper extremity physical function), Timed-Up-and-Go Test (lower extremity physical function), and Short Physical Performance Battery (lower extremity physical function) at treatment completion and less decline at one-month follow-up than usual rehabilitation therapy.

Secondary objective 2: To assess the completion, satisfaction, and adverse event rates of the ADL-enhanced program.

Hypothesis 2a: We hypothesize that the program completion and satisfaction rates will be greater than 75%.

Hypothesis 2b: Fewer patients who receive the ADL-enhanced program will have hospitalizations, emergency room visits, and falls than patients who receive usual rehabilitation therapy at 1-month and 3-month follow-up.

Background and Rationale

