Study design overview. This is a single-blinded, pilot randomized controlled trial of 48 Medicare patients referred to HHC for skilled rehabilitation services. Twenty-four patients will be randomly assigned to the treatment-as-usual arm and receive usual rehabilitation services. The other 24 patients in the experimental arm will receive the ADL-enhanced program in six OT visits as well as usual rehabilitation services.

Selection and Enrollment of Participants

Participants will be recruited from partnered home health agencies

Inclusion criteria. Patients are eligible to the study if they are:

- (1) \geq 65 years of age,
- (2) Medicare beneficiaries,
- (3) referred for skilled rehabilitation services; and
- (4) diagnosed with three or more comorbidities.

Exclusion criteria. Patients are ineligible if they have contraindications for moderate-intensity exercise, which include:

- acute fractures with surgical or weight-bearing restrictions,
- elective joint replacement surgery,
- lower extremity amputation,
- active treatment for cancer diagnosis,
- on-going dialysis treatment,
- acute cardiac surgery,
- acute stroke or a major neurologic disorder limiting motor movements,
- terminal stage of congestive heart failure,
- a referral to hospice care, or
- severe cognitive deficits limiting verbal communication.

Enrollment Procedures.

Screening procedure. The home health care team will obtain verbal permission from new patients to allow the research coordinator to contact and screen the new patients via phone. The coordinator will record the screening results (fail or pass) on a screening log. The coordinator will call the eligible patient, verify the eligibility, and introduce the study.

Consent procedure. The coordinator will then conduct a recruitment home visit to the eligible patient and obtain consent at the end of the visit. If the patient does not provide consent during the recurrent home visit but decides to participate in the study afterwards, a study outcome assessor will obtain consent at the beginning of the baseline assessment visit. Reasons of rejection will be recorded.

Patients who are eligible and agree to participate will be referred to the study outcome assessor, who will schedule the patient within 48 hours to obtain the consent, if not yet obtained by the research coordinator, and complete the baseline assessments (ADL and physical functioning assessments) at the participant's home. The assessor will be blinded to group assignments.

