Randomization. Randomization will occur after the baseline assessment. [name] (Co-I) will generate a randomization list using a computer software and seal the list in opaque envelopes. The on-site research coordinator will open one envelope after a patient has completed the baseline assessments. If the patient is assigned to the ADL-enhanced group, the coordinator will notify the study OT to start intervention.

Post-intervention evaluation.

The satisfaction survey will be given to the patient in the experimental group after the last visit of ADL-enhanced intervention by the research coordinator over the phone.

For the group that will receive the ADL-enhanced program, the post-intervention evaluation conducted by the blinded outcome assessor will occur within seven business days after the completion of the last visit of usual home health rehabilitation therapy or ADL-enhanced intervention, whichever occurs last. For the control group, the post-intervention evaluation conducted by the blinded outcome assessor will occur either 6 weeks after the baseline assessment or after the last usual home health visit, whichever occurs last. Patients will be instructed not to discuss their therapy content with the blinded outcome assessor and vice versa. The following assessments will be administered during the post-intervention evaluation visit.

1. Assessment of Motor and Process Skills
2. Activity Measure of Post-Acute Care Home Health Short Form
3. Jebsen Hand Function Test
4. Box and Block Test
5. Timed-Up-and Go
6. Short Physical Performance Battery
7. Adverse events questionnaire

The research coordinator will extract the patient's OASIS self-care item scores (scores at the start of care and discharge) from medical chart when the patient has been discharged from home health care or 60 days after admission.

One-month follow-up evaluation.

The one-month follow-up evaluation conducted by the blinded outcome assessor will occur within seven business days one month after the completion of the last visit of usual home health rehabilitation therapy or ADL-enhanced intervention (Day 30 post intervention), whichever occurs the last. Patients will be instructed not to discuss their therapy content with the blinded outcome assessor and vice versa. The following assessments will be administered during the one-month follow-up evaluation visit.

1. Assessment of Motor and Process Skills
2. Activity Measure of Post-Acute Care Home Health Short Form

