3. Jebsen Hand Function Test
4. Box and Block Test
5. Timed-Up-and Go
6. Short Physical Performance Battery
7. Adverse events questionnaire

Final evaluation or three-month follow-up evaluation.

The final evaluation will occur over the phone by the research assistant or coordinator within seven days three months after the completion of the last visit of usual home health rehabilitation therapy or ADL-enhanced intervention (Day 90 post intervention). The following assessments will be administered during the final evaluation.

1. Activity Measure of Post-Acute Care Home Health Short Form
2. Adverse events questionnaire

Data analysis plan.

Preliminary analysis. We will compare participant demographics and covariates (e.g., pain levels) between the two groups. Variables with statistically significant differences will be included in the subsequent statistical models as covariates. We will graph spaghetti plots for repeated measurements and examine for outliers.

Data analysis. Since ADL and physical functioning outcomes will be collected over three time points (baseline, post-treatment, one-month follow-up), the mixed-effects linear regression modeling will be conducted to fit the data, in which a random-effects term is included to accommodate within-subject data correlation and a quadratic growth curve is included to describe the temporal trend of the response.

For **Aim 1**, which will estimate the preliminary effect of the ADL-enhanced program on improving ADL, three separate mixed-effects regression analyses will be conducted for the Motor Skills scores of the Assessment of Motor and Process Skills (the primary outcome), the Activity Measure of Post-Acute Care Home Health Short Form, and the OASIS self-care items, in each of which sex, race, age, and other covariates will be included in the model.

For **Aim 2**, which will estimate the preliminary effect of the ADL-enhanced program on physical functioning of the upper extremity and lower extremity, four similar separate analyses will be conducted for the Box and Block Test, Jebsen Hand Function Test, Timed-Up-and Go, and Short Physical Performance Battery.

For **Aim 3**, the program completion rate and satisfaction rate will be compared to the benchmark, 75%. Fisher's Exact Test will be performed to compare the proportion of patients who experience adverse events of hospitalization, emergency room visits, or falls (adverse event rate) between the two groups.

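### The Aim 1 and Aim 2 mixed models leave open how the outcome's own baseline enters; on the usual unconstrained reading the completion effect is unbiased but less precise than the collected data allow

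*Combined protocol and SAP*

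**What the plan says.** The Data analysis paragraph of the Data analysis plan begins: "Since ADL and physical functioning outcomes will be collected over three time points (baseline, post-treatment, one-month follow-up". All three occasions, baseline included, are responses in a mixed-effects linear regression with a random-effects term, and "a quadratic growth curve is included to describe the temporal trend of the response". For the three Aim 1 outcomes the adjustment is described as "in each of which sex, race, age, and other covariates will be included in the model". Aim 2 uses similar analyses for four physical function tests. The Preliminary analysis paragraph adds any variable that differs significantly between the arms.

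No arm term, arm-by-time term or contrast at completion is written out. The outcome's baseline score is not named as a covariate, and no common baseline mean is stated.

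Two other places bear on this. The primary hypothesis is that patients in the experimental arm "will show greater improvements in the Motor Skills scores of the Assessment of Motor and Process Skills (the primary outcome") at completion, which is the language of change. The Randomization paragraph says "Randomization will occur after the baseline assessment", so the expected baseline means are equal in the two arms by design.

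**The concern.** A mixed model with baseline among the responses can give each arm its own baseline mean or give both arms one. The plan does not choose. The first form is the usual default, and its arm-by-time contrast answers a question about improvement directly. It also estimates a baseline arm difference that randomization has already set to zero in expectation, and the noise in that estimate passes into the completion effect. The second form, or the baseline score used as a covariate, avoids this.

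The stated aim is to estimate a preliminary effect in 48 patients, so the width of the interval around the AMPS Motor difference is much of what the trial delivers. While the contrast is unwritten, the choice between estimators with different standard errors also stays open until the data are in hand.

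**Working it through.** **Inputs from the documents (Study design overview).** The trial is a "pilot randomized controlled trial of 48 Medicare patients referred to HHC for skilled rehabilitation services", with 24 in each arm. No derivation of 48 is given, and no effect size, SD, correlation, alpha, power or dropout, so there is no planned figure to reproduce.

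**Assumptions.** SD 1 at each visit; correlation rho between baseline and completion from 0.3 to 0.9; complete data; two-sided 5%; effect 0.6 SD for the power figures. With sex, race and age in the model, SD and rho are those that remain after these covariates.

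**Formulas, n = 24 per arm.**
- Arm-specific baseline means (change-score difference): SE = sqrt[(2/n) × 2(1 − rho)].
- Baseline-adjusted: SE = sqrt[(2/n) × (1 − rho²)], times sqrt[1 + 1/(2n − 4)] = sqrt(1 + 1/44) = 1.011 for the small-sample cost of one covariate.

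Since 2(1 − rho) − (1 − rho²) = (1 − rho)², the adjusted variance is the smaller for every rho below 1, before the small-sample cost.

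**Worked example, rho = 0.5.** Change: sqrt(0.08333 × 1.00) = 0.289. Adjusted: sqrt(0.08333 × 0.75) = 0.250, and × 1.011 = 0.253. Ratio 0.2887/0.2528 = 1.14.

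| rho | SE, change | SE, adjusted | SE, adjusted, with small-sample cost | Excess of change SE over the last |
|---|---|---|---|---|
| 0.3 | 0.342 | 0.275 | 0.278 | 23% |
| 0.5 | 0.289 | 0.250 | 0.253 | 14% |
| 0.7 | 0.224 | 0.206 | 0.208 | 7% |
| 0.8 | 0.183 | 0.173 | 0.175 | 4% |
| 0.9 | 0.129 | 0.126 | 0.127 | 1.5% |

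**Check against the mixed model itself.** Generalized least squares was applied to three visits with a random intercept (equal correlations) and a quadratic time curve by arm. With arm-specific baseline means, the completion contrast has exactly the change-score SE at every rho in the table. With a common baseline mean and baseline still a response, it has exactly the adjusted SE before the small-sample factor (0.250 at rho 0.5, 0.206 at 0.7).

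**Power for 0.6 SD** (noncentral t, 46 df for change and 45 df for adjusted, small-sample cost included):
- rho 0.5: 53% v 64%
- rho 0.7: 75% v 80%
- rho 0.8: 90% v 92%

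**Half-width of the 95% CI (1.96 × SE, small-sample cost included).**
- rho 0.5: 0.566 v 0.496 SD
- rho 0.7: 0.438 v 0.409 SD
- rho 0.8: 0.358 v 0.343 SD

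**Scope.** These figures apply directly to AMPS Motor and the four Aim 2 tests, which have three visits in the Schedule of Evaluations. That table gives the OASIS items two time points and the Activity Measure four.

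**The case against.** The strongest reply is that the plan is under-specified, not shown to be inefficient. Since it writes no arm terms, nothing in it excludes a common baseline mean, and "in each of which sex, race, age, and other covariates will be included in the model" leaves the other covariates undefined. The unconstrained model is a standard analysis, it is unbiased, and it answers the hypothesis as worded. The gain depends on a correlation the documents do not give and nearly vanishes if that correlation is high.

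All of that stands, and it limits the point to what is left unspecified and what that may cost. It does not remove the point: the permitted models differ in precision, and the more precise one uses data the trial already collects. Reading the undefined covariates as including the baseline score would not settle it, because entering a score as a covariate while it is also a response is not a clean adjustment.

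A reader might go further in four ways that the documents do not support.
- *That modelling baseline as a response is itself the fault.* With a common baseline mean it costs nothing, and baseline information is in the model either way; at worst it is weighted less efficiently.
- *That the plan is committed to a change-score analysis.* This is an inference from the hypothesis and from usual practice, because no contrast is written.
- *That the effect is a raw arm difference at the visit, with a much larger loss at high correlation.* The hypothesis speaks of improvement, so this reading fits poorly.
- *That chance baseline imbalance adds a bias through regression to the mean.* Over repeated randomizations there is none. In a simulation of 400 trials at rho 0.6 with a true effect of 0.6 SD, both models averaged 0.60. Imbalance is the same loss of precision seen in a single trial, and should not be counted twice.

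**Conclusion.** The point holds as a gap in specification with a likely cost in precision. The plan does not say how the outcome's baseline enters the arm comparison. On the usual unconstrained reading, the completion estimate is valid but has a standard error about 14% larger than necessary at rho 0.5 and 7% larger at 0.7. The range is 23% at 0.3 down to 1.5% at 0.9, so the gain runs from material to negligible. It rests on 24 analysed per arm, equal variances, complete data and an assumed rho; the power figures also assume a 0.6 SD effect and two-sided 5%. The calculation does not show the sample size of 48 to be wrong. The change is worth making because it is almost free and fixes the primary contrast in advance.

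**What to change.** In the Data analysis plan, state for AMPS Motor and the four Aim 2 tests that the model has time effects plus arm-by-visit terms at the post-baseline visits only, with no arm difference at baseline, because baseline precedes randomization. With three nominal visits the quadratic curve already fits the visit means exactly, so replacing it with visit effects loses nothing. Name the arm difference in AMPS Motor at treatment completion, with its 95% CI, as the primary result.

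An alternative is to model the post-baseline visits only, with the baseline score as a covariate. This drops patients who have only a baseline value, whereas the common-baseline form keeps them.

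For the Activity Measure, use the common-baseline form over its four scheduled visits. For the OASIS self-care items, use ANCOVA of the later score on the start-of-care score.

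The cost is one or two sentences of text and one changed model line, with no new data, patients or visits.

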
Randomization procedure. [name] (Co-I) will generate a randomization list using a computer software and seal the list in opaque envelopes. The on-site research coordinator will open one envelope after a patient has completed the baseline assessments. If the patient is assigned to the ADL-enhanced group, the coordinator will notify the study OT to start intervention.

Study Intervention.

Description of ADL-enhanced intervention. The experimental arm will receive the enhanced-ADL program in 6 home visits from a study OT in addition to usual rehabilitation therapy. The 6 study visits will be delivered over

a 6-week period. The study OT visits will occur separately from usual therapy visits. If the patient cancels a study OT visit, the visit will be rescheduled. The patient will have a 21-day window to resume the intervention. The study OT will apply the compensatory approach in the first 2 visits and the restorative approach in the other 4 visits. Both approaches respect and incorporate the patient's activity preferences in the patient-centered treatment plan. The study OT and the patient collaborate to identify and address ADL tasks that are important and meaningful for the patient's independence.

Compensatory approach procedures. The study OT will conduct a semi-structured interview in the 1st visit to understand the patient's daily routine and to identify two or three ADL tasks that are meaningful but difficult for the patient because of reduced intrinsic capacity. The study OT and the patient collaboratively decide which energy conservation techniques to apply. The patient practices applying these techniques to the selected ADL tasks. The patient is instructed to carry out these ADL tasks with practiced energy conservation techniques until the next visit.

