Restorative approach procedures. The study OT will deliver the restorative approach starting at the 3rd visit. The selected self-care tasks include any in-home activities that the patient does to take care of self and others, which are not limited to basic ADL. In the beginning of each visit, the study OT and the patient together identify 2 or 3 activities where the patient has experienced limitations or difficulties. The study OT will apply one or two activity grading principles to each selected activity. The intervention intensity will be kept at the moderate level (somewhat hard) using the Omni Scale, which is a rated perceived exertion scale. For example, if a patient experiences difficulty to returning pantry items to overhead shelves, the study OT can let the patient wear a weighted wrist cuff while sorting pantry items (increase the load), restore items to an overhead versus shoulder-high shelf (increase the movement distance), restore items into different locations on the shelves (change of movement direction), speed up while storing items (increase the movement speed), store 10 pantry items versus store five items at a time (increase the endurance), or carry groceries with a shopping bag and store pantry items from the groceries to the overhead shelves (increase the activity complexity by combining two tasks, carrying groceries and sorting the pantry items after shopping). Patients will practice each selected task for 15 to 20 minutes with a rest break if needed.

Allowed interventions. All participants will receive the care plan approved by their home health agency. The care plan should include regular home health rehabilitation therapy.

Adherence Assessment. The adherence for the ADL-enhance intervention will be evaluated by the number of sessions that the patient is able to complete within the study period (60 days).

Study Procedures.

[figure not shown]
6.1. Schedule of Evaluations.

	Baseline	Post-intervention (Post intervention \pm 7 Business days) ⁺	One-month follow-up (Day 30 post intervention \pm 7 Business days)	3-month follow-up (Day 90 post intervention \pm 7 Business days)
Assessment of Motor and Process Skills	x	x	x	
Activity Measure for Post-Acute Care Home Health Short Form	x	x	x	x
OASIS self-care items from chart review	x	x		
Box and Block Test	x	x	x	
Jebesen Hand Function Test	x	x	x	
Timed-Up-and-Go Test	x	x	x	
Short Physical Performance Battery	x	x	x	
PEG three-item scale	x			
Patient Health Questionnaire-9	x			

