Saint Louis University Mental Status Exam	x			

Patient demographic background and medical info from self-report as well as chart review	x			
Patient satisfaction survey		x		
Adverse events (hospitalization, falls, emergency room visits)		x	x	x

+: The end of ADL-enhanced program, the last home visit of usual care, or 6 weeks from the baseline assessment, which occurs last.

Study visit schedule.

Description of Evaluations.

Screening evaluation.

The screening will occur over the phone within three business days after a home health care provider has mentioned the study opportunity to the patient and received verbal permission from the patient for the research coordinator to contact him/her. The research coordinator will follow a phone script approved by the UF IRB for this phone screening. The coordinator will obtain a verbal permission prior to proceeding with screening questions from the potential research participant after a brief introduction of the study. These screening questions are:

1. Are you aged 65 years or above?
2. How many medical conditions, including chronic conditions, that you currently have? Examples of the conditions include but not limit to diabetes, heart disease, high blood pressure, joint disease or arthritis, and lung disease.
3. Do you have any of the following conditions?
 - an elective joint replacement surgery in the last month
 - orthopedic or heart surgery in the last month
 - lower extremity amputation
 - currently receiving treatment for cancer
 - an ongoing dialysis treatment
 - a neurologic condition, such as stroke or Parkinson's disease, that significantly limits your movements
 - congestive heart failure that is at the terminal stage

In addition to these questions, the interviewer will administer the "Six-item cognitive screener" to determine the potential participant's cognitive ability. If a participant scores a 4, 5, or 6 on the screener, they will be eligible for the study.

Enrollment, baseline, and randomization.

Enrollment. A patient is considered enrolled in this study when he or she meets the eligibility criteria and signs the informed consent form.

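### The within-patient covariance is left to a single random-effects term; read as a patient intercept, it gives every visit contrast the same standard error, probably too wide for completion to one month and too narrow for baseline to one month, with the direction at completion left open

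*Combined protocol and SAP*

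**What the plan says.** The Data analysis paragraph of the Data analysis plan describes a mixed-effects linear regression over baseline, post-treatment and one month. On dependence within a patient it says only that "a random-effects term is included to accommodate within-subject data correlation". For the means, "a quadratic growth curve is included to describe the temporal trend of the response". It does not say whether the random effect is an intercept alone or also a slope. It names no residual covariance, degrees-of-freedom method, robust variance or fallback. The same model serves Aims 1 and 2.

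Section 6.1 (Schedule of Evaluations) fixes the spacing. A footnote defines the post-intervention point as "The end of ADL-enhanced program, the last home visit of usual care, or 6 weeks from the baseline assessment, which occurs last", so completion falls at least 42 days after baseline. It can fall later: after a cancelled study visit, "The patient will have a 21-day window to resume the intervention". The next assessment in the model is at "Day 30 post intervention", plus or minus 7 business days.

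The hypothesis under the Primary Objective has two parts: more improvement by completion, and less decline afterwards. The Study design overview gives 48 patients, 24 per arm.

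**The concern.** A random intercept with independent residuals implies equal variances at all visits and the same correlation between every pair. The model then pools one within-patient variance and uses it for every change between visits.

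The schedule makes equal correlation doubtful. The first interval is a period of active rehabilitation, in which some patients may gain and others not. The second is shorter and starts after therapy has ended. The two post-treatment visits may well agree more closely with each other than with baseline.

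If so, the common standard error is wrong for particular contrasts. The contrast from completion to one month, which carries the less-decline half of the primary hypothesis, gets an interval that is too wide and loses power. The contrast from baseline to one month gets one that is too narrow. A pilot whose aim is to estimate a preliminary effect depends on its intervals.

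**Working it through.** There is no figure of the plan's to reproduce: the documents give no correlation, SD, alpha, power or effect size.

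**Inputs from the documents.** 24 per arm; three modelled visits; first interval at least 42 days; second about 30 days.

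**Assumptions.** Unit SD at every visit, complete data, two-sided 5% tests, and means free by visit and arm (which a quadratic over three coded visits, crossed with group, amounts to). All correlations are assumed.

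**Formulas.** Write r_jk for the correlation of visits j and k, and rbar for the mean of the three correlations. For the between-arm difference in change:

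- true SE = sqrt(4(1 − r_jk)/24)
- random-intercept SE = sqrt(4(1 − rbar)/24), the same for every contrast
- ratio = sqrt((1 − rbar)/(1 − r_jk))
- approximate false-positive rate = 2(1 − Φ(1.96 × ratio))

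A ratio below 1 means an interval that is too narrow.

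**Worked case.** Take 0.5 for baseline–completion, 0.8 for completion–one month and 0.5 for baseline–one month, so rbar = 0.6.

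- Model SE = sqrt(1.6/24) = 0.258 for all three contrasts.
- True SE = sqrt(2.0/24) = 0.289 for both contrasts with baseline, and sqrt(0.8/24) = 0.183 for completion to one month.
- Ratios are 0.258/0.289 = 0.89 and 0.258/0.183 = 1.41.

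**Other sets**, in the same order of correlations. Cells show the ratio, then the approximate false-positive rate.

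| Correlations | Baseline to completion | Completion to one month | Baseline to one month |
|---|---|---|---|
| 0.5, 0.8, 0.5 | 0.89, 8.0% | 1.41, 0.6% | 0.89, 8.0% |
| 0.6, 0.9, 0.6 | 0.87, 9.0% | 1.73, 0.1% | 0.87, 9.0% |
| 0.7, 0.8, 0.7 | 0.94, 6.5% | 1.15, 2.4% | 0.94, 6.5% |
| 0.6, 0.8, 0.5 | 0.96, 6.1% | 1.35, 0.8% | 0.86, 9.3% |
| 0.7, 0.8, 0.6 | 1.00, 5.0% | 1.22, 1.6% | 0.87, 9.0% |
| 0.7, 0.8, 0.5 | 1.05, 3.9% | 1.29, 1.1% | 0.82, 11.0% |

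Simulation with 20,000 trials per set, using the pooled within-patient mean square on 92 degrees of freedom, agrees with these rates to within simulation error. Tests that use each contrast's own variance stay at about 5%.

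**Power for completion to one month, first set, true difference 0.4 SD.** With its own SE: Φ(0.4/0.1826 − 1.96) = 0.59. With the pooled SE: Φ((0.4 − 1.96 × 0.2582)/0.1826) = 0.28.

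**What decides the direction at completion.** The SE is too narrow only if the baseline–completion correlation lies below the average of the other two. Two mechanisms pull in opposite directions.

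- *Unequal response to therapy that persists.* Let V_d be the variance of individual response and V_e the visit-level variance. The change variances are V_d + 2V_e, 2V_e and V_d + 2V_e, with mean (2/3)V_d + 2V_e. The completion SE is then too narrow for any V_d above 0. With V_d from 0.1 to 0.5 and V_e from 0.1 to 0.2, the ratio is 0.87 to 0.97 at completion and 1.08 to 1.63 for completion to one month.
- *Correlation that decays with time.* With a 30-day correlation of 0.7 and a 42-day first interval, the correlations are 0.7^(42/30) = 0.607, 0.700 and 0.7^(72/30) = 0.425. The ratios are 1.04, 1.19 and 0.86. For 30-day correlations from 0.5 to 0.9 the completion ratio is 1.02 to 1.06, slightly too wide. It drops below 1 only when the first interval exceeds about 48 to 57 days, and is still 0.97 to 0.99 at 60 days.

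**The case against.** The strongest reply is that the wording does not say intercept only. In a growth-curve model a patient-level slope is an ordinary reading, and with a slope the correlations are no longer all equal. That stands against saying that the plan forces equal correlation. It does not remove the problem. A population-level fit of intercept plus linear slope (visits at days 0, 42 and 72) to the correlations 0.5, 0.8, 0.5 gives ratios of 0.85 at completion and 1.25 for completion to one month. At 0.7, 0.8, 0.6, where the intercept model is right at completion, the slope model gives 0.94. A linear slope cannot follow divergence during therapy and then a plateau.

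A reader might also infer from the schedule that the effect at completion must look more certain than it is. The documents do not support that. Simple decay over 42 days gives the opposite sign, and ordinary correlation sets give a ratio of 1.00 or above.

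It is also fair to say that this is a pilot with no stated alpha or decision rule, that point estimates are unaffected with complete and balanced visits, and that SDs and correlations by visit can still be read from the raw data when a larger trial is planned. These points limit the consequences to standard errors, intervals and tests. The missing degrees-of-freedom method adds little by itself: the critical value is 1.99 on 92 degrees of freedom and 2.01 on 46.

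**Conclusion.** The point holds in a limited form. The covariance is under-specified, and on the ordinary reading one pooled variance serves contrasts whose true variances probably differ. In every set examined with unequal correlations and the two later visits most alike, the SE for completion to one month was too wide and that for baseline to one month too narrow. The SE at completion may be too narrow, about right or slightly too wide.

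With correlations of 0.5 to 0.7 with baseline and 0.8 to 0.9 between follow-ups, false-positive rates were about 4–9% at completion, 0.1–3% for completion to one month and 7–11% for baseline to one month. These sizes rest on assumed correlations, equal SDs, complete data and the random-intercept reading.

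The three-visit argument does not reach the OASIS self-care items, which are scheduled at two time points only. The documents also do not support reading this as bias in the estimated effects. I would label it a cheap improvement.

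**What to change.** For outcomes in Aims 1 and 2 measured at three or more visits, replace the single random-effects term with an unstructured within-patient covariance over visits and use Kenward-Roger degrees of freedom. Three visits need 3 × 4/2 = 6 covariance parameters. State in advance that, if the model does not converge, a random intercept with small-sample-corrected robust standard errors will be used. Leave the two-visit OASIS items out of this change.

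Each contrast then gets its own SE, whichever direction the error would have taken. In the worked case the SE becomes 0.289 instead of 0.258 for baseline to completion, and 0.183 instead of 0.258 for completion to one month.

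The cost is a few sentences in the analysis plan, a few more covariance parameters to estimate from 48 patients, and slightly wider intervals if the correlations really are equal. Data collection does not change.
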